5.3. SUBJECT WITHDRAWAL AND/OR DISCONTINUATION

Any subject who wishes to discontinue investigational product use or withdraw from participation in the study for any reason is entitled to do so without obligation. The Investigator may also discontinue any subject from investigational product use or from study participation, if deemed necessary.

Investigational product use may be discontinued and any subject may be discontinued from study participation at any time during the study at the discretion of the Investigator or the sponsor for any reason including but not limited to:

1. Occurrence of any medical condition or circumstance that exposes the subject to substantial risk and/or does not allow the subject to adhere to the requirements of the protocol.
2. Any SAE, clinically significant AE, severe laboratory abnormality, intercurrent illness, or other medical condition that indicates to the Investigator that continued participation is not in the best interest of the subject.
3. Subject's decision to withdraw.
4. Any woman who becomes pregnant while participating in the study. Information on the pregnancy and outcome will be requested.
5. Subject's failure to comply with protocol requirements or study related procedures.
6. Termination of the study by the Sponsor, FDA, or other regulatory authorities.

In the event study discontinuation of a randomized subject is necessary, the Investigator should make every attempt to have the subject complete Visit 6 assessments as possible. If a non-serious AE is unresolved at the time of the subject's final study visit, an effort will be made to follow up until the AE is resolved or stabilized, the subject is lost to follow-up, or there is some other resolution of the event. The Investigator should make every attempt to follow all serious adverse events (SAEs) to resolution. The reason for premature discontinuation should be entered onto the Case Report Form (CRF) and recorded in the subject chart.

Subjects who withdraw from the study will not be replaced.

Additionally, the trial or parts of the trial may be discontinued by the sponsor or at the recommendation of the Investigator after consultation with Kala Pharmaceuticals, Inc. This may be based on a significant number of AEs of a similar nature that warrant such action.

5.4. COLLECTION OF DATA

Source documentation for data collected in this study will be maintained at the investigative site. In cases where no source will be used (e.g., subject diary), it will be noted in the Investigator files. The CRF will be electronic (eCRF) and data will be entered from source documentation into the eCRF. After study completion, an archival copy [e.g., Portable Document Format (PDF)] of the eCRF data will be retained by the site.

6. TREATMENT OF SUBJECTS

6.1. INVESTIGATIONAL PRODUCTS TO BE ADMINISTERED

All subjects meeting eligibility criteria at Visit 1 will receive 2 bottles of single-masked investigational product (vehicle). Subjects who continue to meet eligibility criteria at Visit 2 will be randomized to either KPI-121 0.25% ophthalmic suspension or vehicle. One kit of randomized investigational product containing 3 dropper bottles will be allocated to each subject at Visit 2. At Visit 2 (Day 1/Randomization), subjects will receive 2 bottles of double-masked investigational product (KPI-121 0.25% ophthalmic suspension or vehicle). At Visit 4 (Day 15 ± 1 day), subjects will receive 1 additional bottle of double-masked investigational product from the kit allocated. All bottles will be returned to the site at Visit 6 (Day 29 ± 1 day). The investigational product will be stored at the site in a secure area with limited access at controlled room temperature (15-25°C/59-77°F).

Subjects will be asked to administer investigational product QID. Prior to each instillation, subject will be instructed to shake the bottle. The subjects will record the time of administration of each dose of investigational product at the time of instillation ([Appendix 12](#)). Compliance with instillation of investigational product will be reviewed and assessed at each clinic visit.

6.2. CONCOMITANT MEDICATIONS

All medications that the subject has taken 6 months prior to Visit 1 and through Visit 6 or discontinuation from the study will be recorded in the eCRF and the subject chart. The generic name of the drug, dose, route of administration, duration of treatment (including start and stop dates), frequency, indication, and whether or not the medication was taken due to an AE will be recorded for each medication.

6.2.1. Permitted Medications and Therapies

Medications and therapies not specifically excluded in [Section 6.2.2](#) may be taken as necessary.

6.2.2. Medications and Procedures Not Permitted

The following procedures and medications are not allowed for the time periods specified.

Within 14 ± 1 days prior to Visit 1 (Screening) and for the duration of the study:

- Warm compresses
- Lid margin expression

- Lid margin massage

From Visit 1 (Screening) and for the duration of the study:

- Eyelash growth medications
- Eye drops, gels, or artificial tears (including glaucoma medications)
- Any other topical ophthalmic medication
- TNF-blocking agents (e.g. etanercept, adalimumab, infliximab)

Within 48 hours prior to Visit 1 (Screening) and for the duration of the study, initiate or alter use of:

- Oral contraceptives, and female hormone replacement therapy/supplementation

Within 30 days prior to Screening (Visit 1) and for the duration of the study:

- Ocular, inhaled, or intranasal corticosteroids
- Ocular or oral NSAIDs with the exception of low dose aspirin (≤ 81 mg per day)
- Topical ocular antibiotics
- Topical ocular antihistamines or mast cell stabilizers
- Oral antihistamines
- Topical or nasal vasoconstrictors

Within 30 prior to Visit 1 (Screening), have altered or anticipate alteration of:

- Oral dosing of tetracycline compounds (e.g., tetracycline, doxycycline, or minocycline).
- Omega-3 or Omega-6 supplements

Within 60 days prior to Screening (Visit 1) and for the duration of the study:

- Topical cyclosporine (Restasis[®])
- Any form of topical LE

Within 6 months prior to Screening (Visit 1) have altered or anticipate alteration of dosing during the study:

- Anticholinergics
- Antidepressants
- Isotretinoin
- Oral corticosteroids
- Systemic immunosuppressive agents

6.3. INVESTIGATIONAL PRODUCT USE COMPLIANCE

Compliance will be assessed by comparing investigational product accountability records with the dosing information recorded daily by the subject. The site will document this comparison along with verification of the numbers of used and unused investigational product bottles. The number of missed doses as assessed at each clinic visit should be documented in the eCRF.

6.4. DRUG ACCOUNTABILITY

Sponsor study monitors or designees will conduct accountability of investigational product (KPI-121 0.25% ophthalmic suspension, vehicle, or run-in product). Accountability will be ascertained by performing reconciliation between the amount of drug sent to the site and the amount unused at the time of reconciliation.

Clinical trial materials will be shipped to the investigational sites under sealed conditions. Shipment records will be verified by comparing the shipment inventory sheet to the actual quantity of drug received at the site. Accurate records of receipt and disposition of the investigational product (e.g., dates, quantity, subject number, dose dispensed, returned) must be maintained by the Investigator or his/her designee.

Investigational product will be stored at controlled room temperature (15-25°C/59-77°F) in an area limited to controlled access.

At the end of the study, all study materials, including any unused investigational products (KPI-121 0.25% ophthalmic suspension, vehicle, or run-in product), as well as original containers (even if empty), will be returned to the drug-packaging vendor in accordance with sponsor or designee's Standard Operating Procedures (SOPs), following approval by the Sponsor. All returns of investigational product will be documented. The study monitor or designee will verify drug accountability. All drug accounting procedures must be completed before the study is considered complete.

6.5. MAINTENANCE OF RANDOMIZATION AND PROCEDURE FOR BREAKING THE CODE

The sponsor, the project teams at the designated Contract Research Organizations (CROs), and investigative staff responsible for assessments of study endpoints will be masked to investigational product assignments. A dosing coordinator, who is not responsible for study assessments, will be required to dispense and retrieve double-masked, investigational product to the subjects. In case of medical emergency, or occurrence of an SAE, the randomization code may be unmasked and made available to the Investigator, sponsor, and/or other

personnel involved in the monitoring or conduct of this study. In the absence of medical need, the randomization code will not be available to the above individuals until after the study is completed and the database is locked.

In the event of a medical need, the Investigator will treat each subject as needed. Since there is no specific antidote to KPI-121, immediate emergency unmasking is not necessary. If the Investigator feels it is necessary to unmask a subject's assignment after an emergency situation, the Investigator may call the medical monitor and notify the sponsor. The investigational product assignment will be revealed on a subject-by-subject basis with the approval of the medical monitor and sponsor, thus leaving the masking of the remaining subjects intact.

A randomization code will be computer-generated Kala Pharmaceuticals, Inc. or designee. Randomization team members will work independently of other team members at the CRO. Study personnel, study subjects, the sponsor, and project teams at the CROs involved in the study will be masked to investigational product assignments.

7. ASSESSMENT OF EFFICACY

Efficacy assessments include the following:

- Investigator-rated assessment of posterior lid margin hyperemia
- [REDACTED]
- Investigator-rated assessment of conjunctival hyperemia
- Investigator-rated assessment of the character of the meibomian glands' contents
- Investigator-rated assessment of the expressibility of the meibomian glands
- TFBUT
- Corneal Fluorescein Staining
- [REDACTED]
- In-clinic subject-rated assessment of ocular discomfort

8. ASSESSMENT OF SAFETY

8.1. SAFETY PARAMETERS

Safety parameters include:

- Assessment of AEs
- IOP measurements
- Slit-lamp biomicroscopy
- BCVA
- Dilated ophthalmoscopy

8.2. ADVERSE EVENT DEFINITIONS

Adverse Event (AE): Any untoward medical occurrence associated with the use of an investigational product in humans, whether or not considered drug related.

Adverse Reaction (AR): any AE caused by a drug. Adverse reactions are a subset of all suspected adverse reactions where there is reason to conclude that the drug caused the event.

Suspected Adverse Reaction (SAR):

Any AE for which there is a reasonable possibility that the drug caused the AE. For the purposes of IND safety reporting, “reasonable possibility” means there is evidence to suggest a causal relationship between the drug and the AE. A SAR implies a lesser degree of certainty about causality than adverse reaction, which means any AE caused by a drug.

Unexpected: An AE or SAR is considered “unexpected” if it is not listed in the Investigator’s Brochure or is not listed at the specificity or severity that has been observed; or, if an Investigator’s Brochure is not required or available, is not consistent with the risk information described in the general investigational plan or elsewhere in the current application.

Life-threatening: An AE or SAR is considered “life-threatening” if, in the view of either the Investigator or sponsor, its occurrence places the patient or subject at immediate risk of death. It does not include an AE or suspected adverse reaction that, had it occurred in a more severe form, might have caused death.

A SERIOUS ADVERSE EVENT (SAE) is any AE or suspected adverse reaction occurring at any dose that:

- Results in death.
- Is life-threatening.
- Results in a persistent or significant incapacity or substantial disruption of the ability to conduct normal life functions.
- Requires inpatient hospitalization.
- Prolongs inpatient hospitalization.
- Is a congenital anomaly/birth defect.
- Is a significant medical event (i.e., one that may jeopardize the subject or may require intervention to prevent one or more of the other outcomes listed above).

A NON-SERIOUS ADVERSE EVENT is any AE that does not meet the definitions for SAEs as described above.

Each **AE** will be classified as **SERIOUS** or **NON-SERIOUS** using the definitions provided above.

The **SEVERITY** of each AE will be classified as **MILD, MODERATE, or SEVERE**.

The Investigator will review each event and assess its **RELATIONSHIP** to use of investigational product (unrelated, unlikely, possibly, probably, definitely). The AE will be assessed using the following definitions:

Unrelated:

- Event occurring before dosing.
- Event or intercurrent illness due wholly to factors other than investigational product use.

Unlikely:

- Poor temporal relationship with investigational product use.
- Event easily explained by subject's clinical state or other factors.

Possible:

- Reasonable temporal relationship with investigational product use.
- Event could be explained by subject's clinical state or other factors.

Probable:

- Reasonable temporal relationship with investigational product use.

- Likely to be known reaction to agent or chemical group, or predicted by known pharmacology.
- Event cannot easily be explained by subject's clinical state or other factors.

Definite:

- Distinct temporal relationship with investigational product use.
- Known reaction to agent or chemical group, or predicted by known pharmacology.
- Event cannot be explained by subject's clinical state or other factors.

8.3. PROCEDURES FOR AE REPORTING BY THE INVESTIGATOR

AEs will be monitored throughout the study and will be recorded on the CRF with the date and time of onset, date and time of resolution, severity, seriousness, causality (relationship to use of investigational product), treatment required, and the outcome.

To elicit AEs, simple questions with minimal suggestions or implications should be used as the initial questions at all evaluation points during the trial. For example:

- How have you felt since your last assessment?
- Have you had any health problems since your last assessment?

The severity of each AE should be categorized as mild, moderate, or severe.

The causality of use of investigational product in relation to the AE will be assessed by the Principal Investigator after careful medical consideration and categorized as unrelated, unlikely, possible, probable, or definite.

If an AE occurs, the Investigator will institute support and/or treat as deemed appropriate. If a non-SAE is unresolved at the time of the last day of the study, an effort will be made to follow up until the AE is resolved or stabilized, the subject is lost to follow-up, or there is some other resolution of the event. The Investigator should make every attempt to follow SAEs to resolution.

8.4. RESCUE THERAPY

Any subjects not responding adequately to the study medication may be rescued and placed on alternate therapy at the Investigator's discretion at any time. The choice of rescue medication is at the Investigator's discretion. Any subject placed on rescue therapy will discontinue use of the study medication and continue study participation through Visit 6. Rescued subjects will be considered treatment failures, but the need for rescue therapy will not be considered an AE. Rescued subjects experiencing an AE at the time of rescue will be

followed through stabilization or resolution of the AE or the end of the study (whichever comes last).

8.5. SERIOUS ADVERSE EVENT REPORTING BY THE INVESTIGATOR

Serious Adverse Event Reporting

It is the responsibility of the Investigators or their designees to report any event of this nature to the sponsor or a designee within 24 hours of the event being brought to the Investigators' or their staffs' attention. It is also the responsibility of the Investigator to report all SAEs reported at their site to their Institutional Review Board (IRB), as required. The Investigator should make every attempt to follow all SAEs to resolution.

The following information should be provided when an SAE is reported to the sponsor or designee:

1. Protocol Number
1. Site Number
2. Subject Number
3. Subject Demographic information, including:
 - Date of Birth
 - Sex
 - Race
4. Investigational product start date
5. Date of last dose of investigational product
6. Date investigational product reinitiated (if investigational product interrupted)
7. SAE information, including:
 - SAE term (diagnosis only; if known or serious signs/symptoms)
 - Description of SAE/narrative
 - Date/time of onset
 - Severity
 - Outcome
 - Date/time of resolution or death (if duration < 24 hours)
 - Relationship to investigational product
 - Action taken with investigational product
8. Criteria for classifying the event as serious, including whether the SAE:
 - Resulted in death.
 - Was life-threatening
 - Required inpatient hospitalization.
 - Prolonged inpatient hospitalization.
 - Resulted in a persistent or significant incapacity or substantial disruption of the ability to conduct normal life functions.

- Was a congenital anomaly/birth defect
- Important medical events that may not result in death, were not life-threatening, or did not require hospitalization may be considered serious when, based upon appropriate medical judgment, they may jeopardize the patient or subject and may require medical or surgical intervention to prevent one of the outcomes listed in this definition. Examples of such medical events include allergic bronchospasm requiring intensive treatment in an emergency room or at home, blood dyscrasias or convulsions that do not result in inpatient hospitalization, or the development of drug dependency or drug abuse.

9. Concomitant medications
10. Relevant history
11. Possible causes of SAE other than investigational product
12. Copy of AE page from the CRF

NOTE: If an SAE occurs in any study involving KPI-121 0.25% ophthalmic suspension that is unexpected and is determined to be related or possibly related to investigational product, all sites will be notified by the sponsor and each site should report it to its IRB.

9. STATISTICS

9.1. STATISTICAL METHODS

Continuous measures (e.g., age) will be summarized descriptively by the mean, standard deviation, median, minimum and maximum values. Categorical measures will be summarized by the number and percent of subjects.

9.1.1. Subject Disposition, Demographic and Background Characteristics

Subject disposition, demographic characteristics, and background variables will be summarized by study group.

9.1.2. Analysis of Efficacy

The primary analysis population will be the Intent-to-Treat (ITT) population, defined as all subjects randomized, for all analyses [REDACTED]

[REDACTED] A subset of efficacy analyses will be examined for the Efficacy Evaluable (EE) population, the definition of which will be outlined in the Statistical Analysis Plan and finalized prior to unmasking of study data pursuant to clinical data review.

The primary analysis of all ophthalmic efficacy measures will be based on the single study eye for each subject.

[REDACTED] Severity
Assessment Score between the KPI-121 0.25% ophthalmic suspension group and the vehicle group at Visit 4 (based on the mean score for the 3 days prior to Visit 2 and Visit 4); and (2) comparison of mean posterior lid margin hyperemia [REDACTED]

[REDACTED] at Visit 2 between the KPI-121 0.25% ophthalmic suspension group and the vehicle group at Visit 4.

Secondary and exploratory efficacy endpoints will be evaluated as elaborated in [Section 3](#).

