	
Comparison of mean change from baseline (Visit 2) corneal fluorescein staining between the KPI-121 0.25% ophthalmic suspension group and the vehicle group:
 
• Visit 4 as compared to Visit 2• Visit 6 as compared to Visit 2 
Comparison of mean change from baseline (Visit 2) TFBUT between the KPI-121 0.25% ophthalmic suspension group and the vehicle group:
 
• Visit 4 as compared to Visit 2• Visit 6 as compared to Visit 2 
Comparison of mean change from baseline (Visit 2) [REDACTED] Severity Assessment Score between the KPI-121 0.25% ophthalmic suspension group and the vehicle group:
 
• Visit 4 (based on the mean score for the 3 days prior to Visit 4 and Visit 2)• Visit 6 (based on the mean score for the 3 days prior to Visit 6 and Visit 2) 
Comparison of mean change from baseline (Visit 2) [REDACTED] Frequency Assessment Score between the KPI-121 0.25% ophthalmic suspension group and within the vehicle group:
 
• Visit 4 (based on the mean score for the 3 days prior to Visit 4 and Visit 2)• Visit 6 (based on the mean score for the 3 days prior to Visit 6 and Visit 2) 
Comparison of the mean [REDACTED] Severity Assessment Score between KPI-121 0.025% ophthalmic suspension group and the vehicle group
 
• Visit 4 (based on the mean score for the day prior to Visit 4)• Visit 6 (based on the mean score for the day prior to Visit 6) 
Comparison of the mean change from baseline (Visit 2) [REDACTED] Severity Assessment Score between KPI-121 0.025% ophthalmic suspension group and the vehicle group

--	---

	
• Visit 4 (based on the mean score for the day prior to Visit 4 and Visit 2)• Visit 6 (based on the mean score for the day prior to Visit 6 and Visit 2)
Safety Endpoints	
• IOP measurements• Slit-lamp Biomicroscopy• BCVA• Ophthalmoscopy• Adverse Event (AE) monitoring

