3. TRIAL DESIGN

3.1. PRIMARY EFFICACY ENDPOINTS

Comparison of mean [REDACTED] Severity Assessment Score between the KPI-121 0.25% ophthalmic suspension group and the vehicle group:

- Visit 4 (based on the mean score for the 3 days prior to Visit 4)

Comparison of mean posterior lid margin hyperemia [REDACTED]

[REDACTED] at Visit 2 between the KPI-121 0.25% ophthalmic suspension group and the vehicle group:

- Visit 4

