Comparison of mean change from baseline (Visit 2) TFBUT between the KPI-121 0.25% ophthalmic suspension group and the vehicle group:

- Visit 4 as compared to Visit 2
- Visit 6 as compared to Visit 2

Comparison of mean change from baseline (Visit 2) [REDACTED] Severity Assessment Score between the KPI-121 0.25% ophthalmic suspension group and the vehicle group:

- Visit 4 [REDACTED]
- Visit 6 [REDACTED]

Comparison of mean change from baseline (Visit 2) [REDACTED] Frequency Assessment Score between the KPI-121 0.25% ophthalmic suspension group and within the vehicle group:

- Visit 4 [REDACTED]
- Visit 6 [REDACTED]

Comparison of the mean [REDACTED] Severity Assessment Score between KPI-121 0.025% ophthalmic suspension group and the vehicle group

- Visit 4 [REDACTED]
- Visit 6 [REDACTED]

Comparison of the mean change from baseline (Visit 2) [REDACTED] Severity
Assessment Score between KPI-121 0.025% ophthalmic suspension group and the vehicle
group

- Visit 4 [REDACTED]
- Visit 6 [REDACTED]

TABLE 1: SUMMARY OF EFFICACY ENDPOINTS
 (All comparisons will be between the KPI-121 0.25% ophthalmic suspension and vehicle groups)

Evaluation	Comparison	Visit	1°	2°	Exploratory
Investigator-Rated Assessment of Bulbar Conjunctival Hyperemia	Mean change from BL	6 vs. 2			X
████████ Severity	Mean values	4	████████	X	
████████ Severity	Mean values	6	████████		X
████████ Severity	Mean change from BL	4	████████		X
████████ Severity	Mean change from BL	6	████████		X
████████ Severity	Mean values	4	████████		X
████████ Severity	Mean values	6	████████		X
████████ Severity	Mean change from BL	4	████████		X
████████ Severity	Mean change from BL	6	████████		X

Evaluation	Comparison	Visit	1°	2°	Exploratory
Frequency	Mean values	4			X
Frequency	Mean values	6			X
Frequency	Mean change from BL	4			X
Frequency	Mean change from BL	6			X
Corneal Fluorescein Staining	Mean values	4			X
Corneal Fluorescein Staining	Mean values	6			X
Corneal Fluorescein Staining	Mean change from BL	4 vs. 2			X
Corneal Fluorescein Staining	Mean change from BL	6 vs. 2			X
Investigator-Rated Assessment of the Character of the Meibomian Glands' Contents	Mean values	4			X
Investigator-Rated Assessment of the Character of the Meibomian Glands' Contents	Mean values	6			X

Evaluation	Comparison	Visit	1°	2°	Exploratory
Investigator-Rated Assessment of the Character of the Meibomian Glands' Contents	Mean change from BL	4 vs. 2			X

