9.2. SAMPLE SIZE ESTIMATION

A sample size of 71 in each group will have 90% power to detect an effect size of █ using a 2-group t-test with a █ 2-sided significance level.

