9.3. LEVEL OF SIGNIFICANCE

The primary assessment of the dose-response will be evaluated using a 5% level of significance. Since both co-primary endpoints will be required to be significant at the 0.05 level, there is no adjustment needed for multiple comparisons.

All other reported *p*-values will be considered descriptive and hypothesis generating.

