9.4. PROCEDURE FOR ACCOUNTING FOR MISSING, UNUSED, OR SPURIOUS DATA

Any missing, unused, or spurious data will be noted in the final clinical study report. Multiple imputations will be employed to analyze incomplete data sets under the assumption that missing data are, at worst, characterized as missing at random (MAR). The reasons for missing data will be recorded and the impact of these reasons and any treatment group imbalance on the assumption of MAR will be evaluated. Imputation will be carried out only on the co-primary endpoints and time points.

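### The symptom co-primary is worded in two ways: 9.1.2 adds the days before Visit 2 to a score that 3.1 and the synopsis take from the days before Visit 4 only

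*Combined protocol and SAP*

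**What the plan says.** Section 3.1 lists the symptom co-primary as a between-group comparison of the mean Severity score, at "Visit 4 (based on the mean score for the 3 days prior to Visit 4". The synopsis uses the same words.

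Section 9.1.2, which describes the efficacy analysis, numbers the two co-primaries and gives the symptom comparison as "at Visit 4 (based on the mean score for the 3 days prior to Visit 2 and Visit 4". The opening of that sentence is blacked out. The section's closing line refers to Section 3 for the secondary and exploratory endpoints only, not for the primaries.

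In the synopsis, the three-day window naming both visits appears under the exploratory change-from-baseline scores: "Visit 4 (based on the mean score for the 3 days prior to Visit 4 and Visit 2". Section 3.3 lists that endpoint separately from the primary: "Comparison of mean change from baseline (Visit 2) [REDACTED] Severity Assessment Score between the KPI-121 0.25% ophthalmic suspension group and the vehicle group".

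Section 9.3 sets the stakes: "Since both co-primary endpoints will be required to be significant at the 0.05 level", no multiplicity adjustment is made, and all other p-"values will be considered descriptive and hypothesis generating".

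**The concern.** One confirmatory endpoint has two averaging windows in the current text. The mismatch is legible on both sides: whatever the hidden words say, one place names one visit and the other names two.

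Four meanings of the 9.1.2 wording are possible:

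- the words *Visit 2 and* are a stray phrase, and the endpoint is the Visit 4 three-day mean;
- the Visit 2 three-day mean is a baseline covariate for the Visit 4 value;
- the endpoint is the change from Visit 2 to Visit 4;
- read literally, the score is averaged over both windows.

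These are not the same test. The first three estimate the same expected treatment difference in a randomised trial, but with different variances and different p-values. The fourth mixes a pre-treatment score into the outcome and halves the expected difference. Because the trial's positive result needs this test to reach 0.05, the reader of 9.1.2 should not have to guess which one is meant.

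**Working it through.** **Wording, side by side**

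| Place | Endpoint | Window |
|---|---|---|
| Synopsis, primary | Severity, Visit 4 | 3 days before Visit 4 |
| 3.1, primary | Severity, Visit 4 | 3 days before Visit 4 |
| 9.1.2, co-primary (1) | Severity, Visit 4 (lead-in hidden) | 3 days before Visit 2 and Visit 4 |
| Synopsis, exploratory | Severity, change from Visit 2 | 3 days before Visit 4 and Visit 2 |

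Table 1 does not settle the matter, because its Severity rows are partly blacked out and its columns are broken.

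**Inputs for an illustration of size**

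- Section 9.2: "A sample size of 71 in each group will have 90% power" with a two-group t-test. The effect size and the significance level are blacked out there.
- Section 9.3: 5% level, taken here as two-sided.
- Sections 1.4 and 3.5: about 200 randomised, about 1:1, so about 100 per group.
- Assumed, not in the documents: equal SDs at both visits; Visit 2 to Visit 4 correlation ρ = 0.3, 0.5 or 0.7; no treatment difference at Visit 2; no missing data.

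**Step 1. The plan's own figure.** The 71 per group cannot be reproduced outright without the effect size. Solving backwards with the noncentral t, 71 per group, 90% power and two-sided 0.05 give d = 0.548 SD. This is inferred, not stated. At a level of 0.025 the same solution would be 0.597, and at 0.01 it would be 0.655.

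**Step 2. Standardised effect under each reading**, with d = 0.548 on the Visit 4 value:

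- Visit 4 value: d = 0.548.
- Change from Visit 2: same difference, SD multiplied by √(2(1−ρ)). For ρ = 0.3, 0.548/1.183 = 0.463; for 0.5, 0.548/1.000 = 0.548; for 0.7, 0.548/0.775 = 0.707.
- Average over both windows: the difference is halved to 0.274, because Visit 2 precedes randomised treatment, and the SD is multiplied by √((1+ρ)/2). For ρ = 0.3, 0.274/0.806 = 0.340; for 0.5, 0.274/0.866 = 0.316; for 0.7, 0.274/0.922 = 0.297.

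**Step 3. Power at 100 per group, two-sided 0.05**

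| Reading | ρ = 0.3 | ρ = 0.5 | ρ = 0.7 |
|---|---|---|---|
| Visit 4 value | 97.1% | 97.1% | 97.1% |
| Change from Visit 2 | 90.3% | 97.1% | 99.9% |
| Average over both windows | 67% | 60% | 55% |

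A change score loses power against the Visit 4 value only when ρ is below 0.5, and gains above it. Only the literal average gives a serious loss, and it does so at every correlation tried.

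**The case against.** The best defence is that the visible text already points to one answer. The synopsis and 3.1 agree, and 3.1 is the section that defines the endpoints. Section 9.1.2 itself places the comparison at Visit 4. Change from Visit 2 is a separate exploratory endpoint, so reading 9.1.2 as a change score would duplicate it. The hidden lead-in may name Visit 2 as a covariate, or the SAP may settle the point. Averaging a pre-treatment score into the outcome is implausible as an intention. All of this stands, and it makes a drafting slip the likeliest explanation. It does not remove the discrepancy: a change score would contradict 3.1, a covariate is not shown in 3.1 or the synopsis, and a stray phrase is an error to delete.

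A reader might infer three stronger things that the documents do not support.

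- *That the choice of test is open after unmasking, so the 5% error rate is inflated.* Nothing visible permits such a choice, and 9.5 requires deviations from the statistical plan to be described and justified.
- *That the imputation scope in 9.4 changes with the wording.* That section says "Imputation will be carried out only on the co-primary endpoints and time points", but 9.1.2 still gives Visit 4 as the time point of comparison, and the hyperemia co-primary in 3.1 already refers to Visit 2. The inference is too weak to carry.
- *That the plan lacks baseline or stratum adjustment.* The model may be in the blacked-out text or in the SAP, so its absence cannot be asserted.

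**Conclusion.** The point holds as a discrepancy in the definition of a co-primary endpoint that should be reconciled before unmasking. Confidence is high that the two wordings differ. It is not possible to tell from the available text which meaning 9.1.2 intends, although the Visit 4 three-day mean is the best supported.

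The discrepancy is more than clerical because the test is confirmatory under 9.3, and because 9.1.2 taken at face value describes an analysis with about 55 to 67% power where the Visit 4 value has 97.1%. Those figures rest on the inferred 0.548 SD effect, two-sided 0.05, equal SDs, 100 per group and correlations of 0.3 to 0.7. They show how far the readings can diverge; they do not predict this trial's power. Under the likelier readings power is ample.

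**What to change.** Before unmasking, make 9.1.2 match 3.1 and the synopsis by deleting the words *Visit 2 and*, so that the symptom co-primary is the three-day mean before Visit 4 everywhere. If Visit 2 is meant as a baseline covariate, say so in 9.1.2 and keep the Visit 4 three-day mean as the endpoint. Use the same definition in the SAP.

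The cost is one phrase in 9.1.2 and a matching check of the SAP. No extra data, visits or subjects are needed: the Visit 2 three-day mean is already required for the exploratory change score.
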